**Adoption** is identified as the percentage of providers from the PC clinic who deliver alcohol-related care when a Veteran screens positive for unhealthy alcohol use. Specifically, we will use data available in the EHR to examine delivery of brief interventions, consults placed to PC-MHI/clinical pharmacists or specialty addictions treatment and providing pharmacotherapy for AUDs at the provider and clinic level. Rates of alcohol-related care pre-intervention (2019-2022), during the course of the practice facilitation intervention (July 2022-December 2022), after the intervention (e.g., 3- and 6-months post intervention (Jan 1, 2023-March 31, 2023, and Jan 1, 2023-June 30, 2023 respectively) will be used to measure whether adoption rates of alcohol-related care increased over time.

**Maintenance** is defined as the extent to which evidence-based alcohol care becomes routine and part of the PC culture (care sustained over time). Reach and Adoption outcomes using EHR data will be assessed at 12-months post intervention (Jan 1, 2023-Dec. 31, 2023) to examine whether high-quality alcohol care was sustained.

**Effectiveness** is defined as the prevalence of unhealthy alcohol use at 12-months post-intervention (Jan 1, 2023-Dec. 31, 2023) as measured by AUDIT-C scores pulled from the EHR. This variable will also be expressed as a rate with the denominator defined as all Veterans with a visit to PC during the practice facilitation intervention (same as for Reach outcomes). The numerator will be the number of Veterans with an encounter in PC who screened positive for unhealthy alcohol use (AUDIT-C  $\geq$  5) at 12-months post facilitation intervention. While it is unlikely that a pilot study will have a measurable

impact on clinical outcomes, measuring effectiveness will serve as pilot data for a larger trial.

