## **5.2 Recruitment Methods**

Ann Arbor regulatory approval is being requested only for the data analysis portion of AIM 3 (extraction, cleaning, and analysis of AIM 3 outcome data from the VA's electronic health record via the Corporate Data Warehouse). All recruitment, enrollment and intervention activities were completed at the Pittsburgh VA.

Approximately 10,000 Veterans' data will be pulled from the CDW to examine implementation and clinical outcomes. Data to evaluate implementation and clinical effectiveness outcomes will be obtained electronically and securely from already collected administrative databases, using scrambled SSN or Patient ICN to link data together. Data sources will include the CDW, Health Factors (AUDIT-C and Brief Intervention information), Vital Status File to obtain DOB for calculating age of Veterans, and Prescription/Pharmacy information (for data on whether medications for alcohol use disorder were prescribed). Other specific records include: sociodemographics (e.g., sex, gender identity, marital status, indicator of socioeconomic status, race/ethnicity, sexual orientation), past-year diagnoses (Alcohol use disorder diagnosis, Substance use disorder diagnoses, Tobacco use disorder diagnosis, Mental Health disorder diagnosis (Depression, anxiety, PTSD, Bipolar, Psychotic-spectrum)), index of medical complexity (e.g., Charlson index, VA CAN score) utilization of primary care services pre-implementation (2019-2022), during (July 2022 - Dec. 2022) and post-implementation intervention (Jan 2023 - Dec. 2023), referral and utilization of substance use services in the past year (yes/no), and referral and utilization of past-year mental health services (yes/no). Data may also be reviewed within CAPRI/Joint Legacy Viewer (JLV) to allow study team members to look into potential data anomalies from our dataset. In addition, members of the study team may review notes, charts, dates of AUDIT-C administration, etc. to verify the accuracy of our Aim 3 dataset.

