#### **5.7 Data Analysis**

**Implementation Outcomes:** Reach outcomes will be reported descriptively (e.g., percentage of patients with an AUDIT-C  $\geq 5$  who were offered a BI or pharmacotherapy for AUD) and compared pre- (2019-2022) and post-implementation (at 3- and 6-months) to see whether Reach of alcohol care increased over time. Adoption outcomes via EHR will be descriptive, and include percentages, frequencies, and means (SD) of alcohol-related care by provider and clinic to understand whether Adoption of high-quality alcohol-related care increased over time. Descriptives will be examined and compared at the start of Active Implementation and at 3- and 6-months post Active Implementation. Reach and Adoption rates will again be examined at 12-months post Active Implementation and compared to rates at 3- and 6-months to see if high-quality alcohol-related care was sustained (Maintenance). **Effectiveness outcomes:** Effectiveness will be assessed via a time-series analysis, where the intervention site will serve as its own control, and we will investigate whether Veterans' with an encounter in Pittsburgh VA Primary Care during the implementation intervention reduced their drinking 12-months post intervention using AUDIT-C scores in the EHR. Time-series analysis was chosen because historical trend is accounted for in the analytic model, results can be displayed graphically, and the size of the effect can be estimated at different times post

intervention. The outcome (AUDIT-C scores) will be modeled using a regression model with an indicator for practice facilitation (pre- vs. post-), a continuous term for time (days since practice facilitation dissemination) and the interaction between the two. The indicator variable will assess immediate changes in AUDIT-C scores post implementation intervention, while the interaction term will assess if there is a change in the slope of AUDIT-C scores pre- and intervention at 12-months. While there is controversy over whether pilot studies should assess clinical efficacy or effectiveness, we decided to examine it here as a training opportunity and as preparation for a possible hybrid effectiveness-implementation Merit trial investigating practice facilitation as a way to improve alcohol-related care on a larger scale.

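### With no month-of-year term in the Effectiveness model, a yearly AUDIT-C cycle that rises or falls across 2023 would be read as a slope change if the post segment is January-December 2023

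*Combined protocol and SAP*

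**What the plan says.** Section 5.7 (Effectiveness outcomes) models AUDIT-C scores by regression on three terms: "an indicator for practice facilitation (pre- vs. post-), a continuous term for time (days since practice facilitation dissemination) and the interaction between the two". An immediate change is to be picked up by the indicator, and "the interaction term will assess if there is a change in the slope of AUDIT-C scores pre- and intervention at 12-months". The clinic is its own control, so there is no comparison series. The method is justified as follows: "Time-series analysis was chosen because historical trend is accounted for in the analytic model". No seasonal term is listed.

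The periods are dated elsewhere. Section 5.1 defines Effectiveness as the "prevalence of unhealthy alcohol use at 12-months post-intervention (Jan 1, 2023-Dec. 31, 2023) as measured by AUDIT-C scores". Section 5.2 gives January-December 2023 as post-implementation and July-December 2022 as a separate active period. Section 5.1 gives the pre-intervention period as 2019-2022, which overlaps the active period. The data pull covers 1 January 2019 to 31 December 2023. Section 5.7 does not give the calendar date at which the indicator switches, and does not assign July-December 2022 to either segment.

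**The concern.** The two slopes being compared rest on very different lengths of time. The pre slope uses 3.5 to 4 years, over which a yearly cycle nearly averages out. On the dates in sections 5.1 and 5.2, the post slope uses a single January-December year, over which it need not. Suppose scores, or the mix of Veterans screened, tend to be higher in spring than in autumn every year. The 2023 line then slopes down for that reason alone. A linear time term removes a linear historical trend but not a cycle, and no control series would reveal it.

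Both coefficients that section 5.7 proposes to interpret are exposed. A regular pattern unrelated to facilitation could appear as a change in slope together with an immediate change of opposite sign. The plan intends this result to inform a larger trial, so a spurious slope in either direction could mislead that planning.

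**Working it through.** **Figure in the plan.** There is none to reproduce. The documents give no alpha, SD, effect size or sample-size calculation for this model.

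**Inputs from the documents.** Model terms from section 5.7; data span, active period and 2023 post period from sections 5.1 and 5.2.

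**Assumed inputs.** An annual cycle of amplitude A points, the same every year; no facilitation effect; independent scores, evenly spread; 5,000-8,000 scores a year; SD 2.0-2.5; a two-sided 5% test.

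**Step 1: slope from one calendar year.** With t in years on [0, 1], the least-squares slope of A sin(2πt) is A x cov(t, sin 2πt) / var(t) = A x (-1/(2π)) / (1/12) = -(6/π)A = -1.91A per year. For A cos(2πt) it is 0. Only the sine part matters. A peak around 1 April gives -1.91A, a peak around 1 October +1.91A, and a peak at the turn of the year or at mid-year about 0.

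**Step 2: subtract the pre slope.**
- July-December 2022 left out (pre is 3.5 years): pre slope at most about 0.012A, so the worst-phase interaction bias is 1.91A.
- July-December 2022 counted as pre (4 years): pre slope -1.91A/4² = -0.12A, so the bias is 1.91A - 0.12A = 1.79A.
- Indicator switching at 1 July 2022 (post is 18 months): fitting the same four-term model to daily data gives 0.20A.

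**Step 3: standard error, July-December 2022 left out.** With n scores a year, the post slope has SE √12 x SD/√n and the pre slope has SE √12 x SD/(3.5 x √(3.5n)).
- n = 8,000, SD 2.0: √(0.0775² + 0.0118²) = 0.078.
- n = 5,000, SD 2.5: √(0.1225² + 0.0187²) = 0.124.

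**Step 4: rejection at A = 0.10.**
- July-December 2022 left out, bias 0.191: z = 0.191/0.124 = 1.54 gives Φ(1.54 - 1.96) = 34%; z = 0.191/0.078 = 2.44 gives Φ(2.44 - 1.96) = 68%. Averaged over all phases: 19% and 39%.
- July-December 2022 counted as pre, bias 0.179, nearly the same SEs: z = 1.44 gives 30% and z = 2.29 gives 63%.
- Switch at July 2022, bias 0.020, SE 0.069 and 0.044: about 6% and 7%.

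**Step 5: sensitivity to A.** July-December 2022 left out, over a wider range of 5,000-10,000 scores a year and SD 2.0-3.0:

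| A (points) | Worst-phase bias (points/year) | Rejection, worst phase | Rejection, phase-averaged |
|---|---|---|---|
| 0.05 | 0.096 | 10-28% | 7-16% |
| 0.10 | 0.191 | 25-78% | 15-45% |
| 0.20 | 0.382 | 73-100% | 42-76% |

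**Step 6: the indicator.** With time measured from 1 January 2023, the worst-phase false jump is 0.86A (July-December 2022 left out) or 1.19A (counted as pre), opposite in sign to the slope bias. At A = 0.10, 5,000 scores a year and SD 2.0, it is rejected 25% or 47% of the time. If time zero is July 2022 but the post data start in 2023, the indicator is extrapolated back half a year. The false jump then becomes 0.86A + 0.5 x 1.91A = 1.82A.

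**Step 7: with seasonal terms.** One sine/cosine pair removes the bias from a sine-shaped cycle. Eleven month indicators leave at most 0.005A under all three segmentations.

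**The case against.** The strongest objection concerns the cut-point. Section 5.7 counts time from dissemination of facilitation and gives no calendar date for the switch. If the indicator turns on in July 2022, the post segment is 18 months, the bias is 0.20A and the problem almost disappears. This stands as a limit on the point: a reader might infer that the model text itself fixes a one-year post segment, and it does not. The 2023 reading comes from sections 5.1 and 5.2. It is still the natural one, because those sections date the post period that way and treat July-December 2022 separately.

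A reader might also infer that any within-year pattern is mistaken for a facilitation effect. Step 1 shows otherwise: a cycle symmetric about mid-year gives essentially no slope bias. The worst-phase rates are roughly double the phase-averaged ones.

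Nor do the documents show that AUDIT-C scores, or attendance, are seasonal at all. Amplitude, phase, SD and scores per year are all assumed, and repeated scores from the same Veterans would change the SEs used here. A long look-back in the questionnaire would damp seasonality in drinking, though not in who attends. These objections limit how large a bias can be claimed. They do not justify fixing the seasonal effect at zero when five years of data can estimate it.

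Finally, the plan calls Effectiveness pilot data, expects no measurable clinical impact and sets no significance rule. That is correct, and it limits the consequence.

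**Conclusion.** The point holds conditionally. If the post segment is January-December 2023, the stated model cannot separate a slope change from the part of an annual cycle that rises or falls across the year. The worst-phase bias is about 1.9 or 1.8 points per year per point of amplitude, depending on whether July-December 2022 is left out or counted as pre. The rejection rates rest on the assumed amplitude, score counts, SD and independence; the bias multipliers rest only on the design and a sine-shaped cycle that repeats each year. If the switch is at July 2022, the bias is about a tenth as large.

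A reader might take this to mean that the trial's main test would fail. The documents do not support that: no confirmatory decision hangs on this interaction. The realistic harm is a misleading exploratory slope and jump carried into the planning of a larger trial. The change is worth making because it is cheap and works whichever cut-point is chosen.

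**What to change.** In section 5.7, add one sine/cosine pair with a one-year period, or 11 month-of-year indicators, estimated jointly over 2019-2023. Read the indicator and the interaction from that model. State the calendar date at which the indicator switches, the date of time zero, and whether July-December 2022 is pre, post, a separate segment or excluded. Reconcile this with the pre-intervention period given as 2019-2022.

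The cost is SAP wording and 2 or 11 extra parameters. No new data are needed, and the analysis is still to be done. With a 2023 post segment, the SE of the slope change rises about 6-8% with the harmonic pair (for example 0.099 to 0.107 at 5,000 scores a year, SD 2.0, July-December 2022 left out) or 11-13% with month indicators (0.099 to 0.112 in the same case). The terms remove only a pattern that repeats from year to year; one peculiar to 2023 would remain.

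### Section 5.7 asks about drinking at 12 months, but neither coefficient it interprets measures the 12-month effect; the combination that does is not made the Effectiveness result

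*Combined protocol and SAP*

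**What the plan says.** The Effectiveness part of section 5.7 sets the question as whether Veterans seen in the clinic during the intervention "reduced their drinking 12-months post intervention using AUDIT-C scores in the EHR".

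The model begins with a period term: the outcome "will be modeled using a regression model with an indicator for practice facilitation (pre- vs. post"). Two further terms, one for calendar trend and one for its change between periods, complete the model and are described as "a continuous term for time (days since practice facilitation dissemination) and the interaction between the two".

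Two terms are given a meaning:
- Indicator: "The indicator variable will assess immediate changes in AUDIT-C scores post implementation intervention".
- Interaction: "the interaction term will assess if there is a change in the slope of AUDIT-C scores pre- and intervention at 12-months".

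Among its reasons for choosing time-series analysis, section 5.7 says that "the size of the effect can be estimated at different times post" (that is, after facilitation). It does not name any of those time-specific effects as the result.

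Section 5.1, in the evaluation of outcomes, has Effectiveness "defined as the prevalence of unhealthy alcohol use at 12-months post-intervention (Jan 1, 2023-Dec. 31, 2023"). It dates active facilitation as "during the course of the practice facilitation intervention (July 2022-December 2022"). Section 5.7 does not say whether those six months count as pre, post or neither, and it gives no calendar date for day zero.

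**The concern.** The question concerns one time, 12 months. The two interpreted terms concern something else: a gap at the time origin, and a rate of change per day. The words at 12 months are attached to the rate, yet in a linear model that rate is the same at every post-intervention date.

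Two analysts could therefore take the same fitted model and answer the 12-month question differently. One might look to the interaction because it carries the 12-month label. Another might look to the indicator because it is the pre/post comparison. Neither would be reporting the size of the effect at 12 months or its uncertainty, which is what a larger trial would need from this pilot.

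**Working it through.** The plan states no power, alpha, SD or effect size for this analysis, so there is no figure to reproduce. The first step is algebra and needs no outside number.

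**1. The model in section 5.7**

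E[Y] = b0 + b1·post + b2·t + b3·post·t

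The post-period line minus the projected pre-period line at day t is b1 + b3·t. Hence:
- b1 is the effect at t = 0 only.
- b3 is the change in that effect per day, the same at every t.
- The 12-month effect is b1 + b3·t12.
- Its variance is Var(b1) + t12²·Var(b3) + 2·t12·Cov(b1, b3), so its interval cannot be read off the two separate coefficients.

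**2. What t12 is**

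The follow-up window ends on 31 December 2023. If day zero is 1 January 2023, t12 = 364. If day zero is 1 July 2022, t12 = 364 + 184 = 548. The plan does not choose.

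**3. Three patterns, with day zero and the post-period both starting on 1 January 2023**

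Take a 0.3-point change.
- Immediate and lasting: b1 = -0.30, b3 = 0. Effect at day 364: -0.30.
- Immediate, then fading linearly to zero: b1 = -0.30, b3 = 0.30/364 = +0.00082 a day. Effect at day 364: -0.30 + 0.30 = 0. Mean effect over 2023: -0.15.
- Gradual fall: b1 = 0, b3 = -0.00082 a day. Effect at day 364: -0.30.

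**4. Illustrative size**

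Taken from the documents: data from January 2019 to December 2023, facilitation July-December 2022, follow-up in 2023. Assumed: SD 2.5; 4,000 to 10,000 scores a year, evenly spread; independent errors; July-December 2022 left out; two-sided 5% level. Variance = SD²·(X'X)⁻¹.

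| Scores a year | SE of b1 | SE of b3, per year | SE of 12-month contrast |
|---|---|---|---|
| 4,000 | 0.094 | 0.139 | 0.107 |
| 7,000 | 0.071 | 0.105 | 0.081 |
| 10,000 | 0.060 | 0.088 | 0.067 |

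Probability that each quantity is significant, from 4,000 to 10,000 scores a year:

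| Pattern | b1 | b3 | 12-month contrast | True 12-month effect |
|---|---|---|---|---|
| Lasting | 0.89-1.00 | 0.05 | 0.80-0.99 | -0.30 |
| Faded | 0.89-1.00 | 0.58-0.93 | 0.05 | 0 |
| Gradual | 0.05 | 0.58-0.93 | 0.80-0.99 | -0.30 |

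Only the contrast follows the last column in all three rows.

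**5. Sensitivity**

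In the faded pattern at SD 2.5, going from 5,000 scores a year with a 0.2-point change to 10,000 with 0.5 points, b1 is significant with probability 0.66-1.00 and b3 with 0.37-1.00.

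**6. Time origin**

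Suppose the post-period starts on 1 January 2023 but days are counted from 1 July 2022. In the faded pattern b1 becomes -0.30 - 184 × (0.30/364) = -0.45. It is then a back-projection of 184 days and no longer the immediate change. The effect on 31 December 2023 is still zero: -0.45 + 548 × (0.30/364) = 0 (0.45 in both terms). A contrast at a fixed calendar date does not depend on the origin; b1 does.

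**The case against.** A reader might infer that the planned terms would give the wrong answer: that a lasting reduction would be missed, or a vanished one declared. The documents do not support that.
- A lasting drop shows clearly on the indicator, with power at least that of the contrast (0.89-1.00 against 0.80-0.99). It is missed only by someone who ignores a term the plan interprets.
- A faded drop gives a negative indicator and a positive interaction, and section 5.7 also foresees graphical display. A careful reader would see the fade.
- Section 5.7 states no significance level or success rule, so no declaration is built in. Significance in the faded pattern is likely under the assumptions above, but not assured.

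It can also be said that 12 months is a window in section 5.1, January to December 2023, and that the slope wording may mean no more than slope over that window. On that reading the faded pattern has a real mean reduction of 0.15 points. A contrast at 31 December alone would miss it, while a window average would detect it with power 0.54-0.90. This stands, and it is why the window average belongs beside the end-date estimate.

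Finally, the plan says that effects at different times can be estimated. That is true, and it means the model need not change. But the statement is a reason for choosing the method; no such effect is named as the result. Opposite signs suggest a fade without showing whether any effect remains at 12 months, which needs the sum and its covariance-based interval.

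**Conclusion.** The mismatch between question and interpreted terms holds, by algebra alone. The interaction is not a 12-month measure, neither coefficient alone answers the 12-month question, and the quantity that does is not specified as the Effectiveness result. The model itself is adequate for producing it.

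The percentages are illustrative. They rest on an assumed SD, score count, effect size, 5% level and independent errors, and on leaving out July-December 2022. Repeated scores per Veteran would alter the standard errors but not the algebra.

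Severity is moderate. Section 5.1 calls a measurable clinical impact unlikely and treats the result as pilot data, and no decision depends on it. The contrast is on the AUDIT-C score scale, so it does not by itself deliver the prevalence of scores of 5 or more that section 5.1 defines as Effectiveness.

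**What to change.** In section 5.7:
1. Make the Effectiveness estimate the indicator plus the interaction times the days from the time origin to 31 December 2023, with its SE from the coefficient covariance matrix and a 95% CI.
2. Report the same contrast at 3 and 6 months, and averaged over January-December 2023.
3. Keep the indicator and interaction as supporting results, and remove the reference to 12 months from the reading of the interaction.
4. State the calendar date of day zero and whether July-December 2022 is pre, post or excluded. These set the elapsed days and the meaning of the indicator.

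Cost: a few sentences and a linear-contrast command. The documents describe the outcome analysis as still to be done, so this is feasible.

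Two downsides should be stated. The end-date contrast is slightly less precise than the indicator (SE about 0.07-0.11 against 0.06-0.09 under the assumptions above). It also relies on projecting the pre-period line about 18 months, from June 2022 to December 2023, so it depends on that line staying straight.

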## **5.8 Withdrawal of Subjects**

Not applicable.

## **6.0 Reporting**

In the unlikely event that a data breach occurs, the study team will notify the Ann Arbor VA IRB, Privacy Officers, and Information System Security Officers as soon as the breach is identified.

## **7.0 Privacy and Confidentiality**

All study staff accessing the data is approved for VA research and are up-to-date on all mandatory annual trainings in data security and human subjects protections and are educated in the use of all data security procedures necessary to ensure patient privacy and data security. All information will be maintained in accordance with the security requirements of 38 CFR section 1.466 or more stringent requirements. The data analyst will be responsible for creating analytic datasets for investigators; these datasets will be de-identified per HIPAA guidelines. All resulting research data will be presented in aggregate only and will not identify any individual patient in any report of the research, or otherwise disclose patient identities. No data will be disclosed outside the VA.

